### **5.3 Efficacy Pharmacokinetic, Pharmacodynamic, Exploratory Research and Validation Studies, and Safety Assessments/Variables**

#### **5.3.1 Efficacy and Safety Measurements Assessed and Flow Chart**

Study procedures described are listed in the following section of this protocol and are summarized in tabular format in [Appendix D](#), [Appendix E](#), and [Appendix F](#).

Study visits may be impacted by cases of state of emergency or pandemic situations like COVID-19. This may include changes such as virtual visits, visits at alternative locations, or changes in the visit frequency and timing of study procedures, among others. Additional details are provided in Section [5.3.1.1](#).

Every effort should be made to ensure the safety of subjects and site staff, while maintaining the integrity of the study.

Supplemental study case report forms should be completed in the event of missed/virtual visits, or study drug interruptions or discontinuations related to COVID-19.

Study Visits and/or activities should be performed as scheduled whenever possible. During a state of emergency or pandemic situation, if it is not possible for all study procedures to be performed as specified due to travel restrictions or other reasons, the following modifications are allowed:

- If permitted by local regulations, the IRB/IEC and the subject, study visits may be conducted in a subject's home residence (see Section [5.3.1.1](#) – Sub-Section "Optional Home Healthcare Service Due to State of Emergency or Pandemic Situation like COVID-19").
- The following study activities may be performed virtually by phone/video conference:
  - Adverse event assessment
  - Concomitant therapy assessment including compliance to contraception requirements, if applicable

- Latent TB risk assessment
- Communication of in-home urine pregnancy test result
- Dispense study drug and subject dosing diary (see Section 5.3.1.1 - Sub-Section "Study Drug Dispensing, Dosing, and Compliance" for details about the Direct-to-Patient shipment)
- Review of subject dosing diary, compliance to IP administrations
- During a virtual visit, the following activities should not be performed:
  - Patient questionnaires
  - X-rays (bilateral hands/feet)
  - Vital signs and body weight
  - Physical exam
  - Physician Global Assessment (PhGA)
  - TJC68/SJC66
- The following study activities may be performed by a local clinic/hospital/laboratory:
  - QuantiFERON-TB Gold test or equivalent (and/or local PPD skin test)
  - Chest x-ray, if the Investigator has determined, based on clinical judgement, that a CXR is required to ensure that it is safe to continue study drug administration (e.g., subjects with seroconversion on an annual TB test).

In this case, CXR should be performed as soon as restrictions allow at the study site or local hospital/facility. Otherwise, the CXR will be performed at the next earliest feasible visit.
  - 12-lead ECG, if the Investigator has determined, based on clinical judgement, that an ECG is required to ensure that it is safe to continue study drug administration In this case, ECG should be performed as soon as restrictions allow at the study site or local hospital/facility. Otherwise, the ECG will be performed at the next earliest feasible visit.
  - Local urine pregnancy test
  - Lab tests (blood chemistry, hematology, urinalysis)
  - ESR

All procedures performed at local facilities must be performed by appropriately qualified personnel.

- Lab draws should be obtained as close as possible to the scheduled visit.
- The study site should keep records of all visits/study activities performed virtually by phone/video or through the optional Home Healthcare Service or by a local clinic/hospital/laboratory.

### **5.3.1.1 Study Procedures**

The study procedures outlined in [Appendix D](#) and [Appendix F](#) are discussed in detail in this section, with the exception of exploratory research and validation studies (discussed in Section [5.3.1.2](#)), drug concentration measurements (discussed in Section [5.3.2](#)), the collection of prior and concomitant medication information (discussed in Section [5.2.3](#)), and the collection of AE information (discussed in Section [6.0](#)). All study data will be recorded in source documents and on the appropriate eCRFs.

#### **Informed Consent**

At the Screening Visit, the subject will sign and date a study specific, IEC/IRB approved, informed consent form for the study (i.e., includes both Periods 1 and 2) before any study procedures are performed or any medications are withheld from the subject in order to participate in this study. Separate written consent will be required for each subject in order to participate in the optional exploratory research and validation studies. The separate written consent may be part of the main consent form. Subjects can withdraw informed consent at any time.

Details regarding how informed consent will be obtained and documented are provided in Section [9.3](#).

#### **Inclusion/Exclusion Criteria**

Subjects will be evaluated to ensure they meet all inclusion criteria and have none of the exclusion criteria at both Screening and Baseline Visits.

### **Medical and Surgical History**

A complete non-RA-related medical and surgical history, including history of alcohol and nicotine use, will be taken from each subject during the Screening Visit. Additionally, a list of each subject's specific RA-related medical and surgical history will be recorded at Screening. History of herpes zoster, herpes zoster vaccination, and hepatitis B vaccination status will be recorded as part of the medical history. An updated medical history will be obtained prior to study drug administration at Baseline, to ensure the subject is still eligible for enrollment.

A detailed medical history with respect to TB risk factors will be documented in the study source documentation. This information will include BCG vaccination, cohabitation with individuals who have had TB, and travel to, residence in, or work in TB endemic locations.

### **Patient Questionnaires**

Subjects will complete the following questionnaires as specified in [Appendix D](#) and [Appendix F](#); a validated translation will be provided in their local language, as applicable:

#### *Period 1*

- Patient's Global Assessment of Disease Activity Visual Analog Scale (VAS) ([Appendix J](#))
- Patient's Assessment of Pain VAS ([Appendix K](#))
- Health Assessment Questionnaire – Disability Index (HAQ-DI) to assess the physical function and health-related quality of life of each subject ([Appendix L](#))
- Patient's Assessment of Severity and Duration of Morning Stiffness Numerical Rating Scale (NRS) ([Appendix M](#))\*
- EuroQoL-5D-5L (EQ-5D-5L) ([Appendix N](#))
- Functional Assessment of Chronic Illness Therapy – Fatigue (FACIT-F) ([Appendix O](#))

- Work Productivity and Activity Impairment (WPAI) ([Appendix P](#))
- Short Form-36 (SF-36) ([Appendix Q](#))

*Period 2*

- Patient's Global Assessment of Disease Activity VAS ([Appendix J](#))
- Patient's Assessment of Pain VAS ([Appendix K](#))
- HAQ-DI to assess the physical function and health-related quality of life of each subject ([Appendix L](#))
- Patient's Assessment of Severity and Duration of Morning Stiffness NRS ([Appendix M](#))\*

\* Paper; all other patient-reported outcomes (PROs) collected electronically.

The subject should complete the questionnaires before site personnel perform any clinical assessments and before any interaction with site personnel has occurred to avoid biasing the subject's response.

Due to a state of emergency or pandemic situation like COVID-19, subject visits may be conducted via phone or video conference. In these situations, questionnaires will be completed by the subject at the next feasible visit.

**TB Testing/TB Prophylaxis**

The TB screening tests are diagnostic test results to be interpreted in the context of the subject's epidemiology, history, exam findings, etc., and it is the responsibility of the Investigator to determine if a subject has previous, active, or latent TB.

At Screening, all subjects will be assessed for evidence of increased risk for TB by a risk assessment form ([Appendix I](#)) and tested for TB infection by QuantiFERON-TB Gold test. The PPD skin test should be utilized only when a QuantiFERON-TB Gold test is not possible for any reason (unless both tests are required per local guidelines). The site staff will complete the TB risk assessment form and enter the data into an appropriate eCRF.

If a subject had a negative QuantiFERON-TB Gold (and/or PPD) test (or IGRA equivalent such as T-SPOT TB test) within 90 days prior to Screening and source documentation is available, the test does not need to be repeated, provided nothing has changed in the subject's medical history to warrant a repeat test. These cases may be discussed with the AbbVie Therapeutic Area Medical Director. The results of the TB test(s) will be retained at the site as the original source documentation.

For subjects with a negative TB test result at Screening or most recent evaluation, an annual TB re-test will be performed. The TB test(s) to be performed depends on local guidelines and whether or not the site has capacity to perform QuantiFERON-TB Gold testing (see below). If an annual TB test is newly positive (seroconversion), a chest x-ray (CXR) needs to be performed as soon as possible to aid in distinguishing active versus latent TB. Expert consultation can be considered per Investigator's discretion. Any positive TB test result after the patient has started study drug should be reported as an adverse event (AE).

*TB Test:*

- For regions that require both PPD and QuantiFERON-TB Gold testing, both will be performed. A positive TB test is defined by local guidelines (for example, in some countries, both PPD and QuantiFERON-TB Gold are performed, and if either one is positive, the TB test is considered positive).
- In the absence of local guidelines defining a positive result when both PPD and QuantiFERON-TB Gold tests are performed, then the QuantiFERON-TB Gold test result will be the TB test result (QuantiFERON supersedes PPD).
- If a site has the capacity to perform both PPD and QuantiFERON-TB Gold tests, and local guidelines require only one test to be performed, then the QuantiFERON-TB Gold is the preferred test. At a site with capacity to perform both tests, whatever TB test method (i.e., PPD or QuantiFERON-TB Gold or other IGRA) was performed at screening, then the subject should have their annual TB test performed with the same test method.
- If QuantiFERON-TB Gold test is NOT possible (or if both the QuantiFERON-TB Gold test and the PPD skin test are required per local

guidelines): the PPD skin test (also known as a TB skin test) will be performed according to standard clinical practice. The TB skin test should be read by a licensed healthcare professional between 48 and 72 hours after administration. A subject who does not return within 72 hours will need to be rescheduled for another skin test. The reaction will be measured in millimeters (mm) of induration and induration  $\geq 5$  mm for RA subjects is considered a positive reaction. The absence of induration will be recorded as "0 mm" not "negative." Subjects who have had an ulcerating reaction to the TB skin test in the past should not be re-exposed and the TB Skin Test should be considered positive with no requirement for subsequent testing with either PPD or QuantiFERON-TB Gold test.

- If the QuantiFERON-TB Gold test is indeterminate, then the investigator should perform a local QuantiFERON-TB Gold test (or through the central laboratory if not locally available) to rule out a positive test result. If testing remains indeterminate or is positive, then the subject is considered to be positive for the purpose of this study. If the testing result is negative, then the patient is considered to be negative.
- Interpretation of a positive annual TB test in low risk subjects: In cases where the QuantiFERON-TB Gold test by the central laboratory is positive and the Investigator considers the subject at low risk for TB and has no clinical suspicion of TB, the Investigator may perform a local QuantiFERON-TB Gold test (or repeat testing through the central laboratory if not locally available) to confirm the positive test result. If the repeat testing result is negative, the Investigator may consider the test to be negative based on his/her clinical judgment; if the repeat testing result is positive or indeterminate, the test is considered positive.
- An equivalent Interferon Gamma Release Assay (IGRA) (such as T-SPOT TB test) may be substituted for the QuantiFERON-TB Gold test.
- Subjects with documentation of prior positive result of QuantiFERON-TB Gold Test (or equivalent) and/or PPD are not required to repeat either test during the study and should be considered positive. Annual TB questionnaire should be completed for ALL subjects.

Subjects with a negative TB test and CXR not suggestive of active TB or prior TB exposure may be enrolled.

Subjects with a positive TB test must be assessed for evidence of active TB versus latent TB, including signs and symptoms and CXR. Subjects with no signs or symptoms and a CXR not suggestive of active TB may be enrolled after initiation of TB prophylaxis (see below). Subjects with evidence of active TB may not be enrolled.

*TB Prophylaxis:*

At Screening, if the subject has evidence of a latent TB infection (positive TB test and the subject has a CXR not suggestive of active TB), prophylactic treatment must be initiated at least 2 weeks prior to administration of study drug (or per local guidelines, whichever is longer). The prophylaxis needs to be completed; however, the full course of prophylaxis does not need to be completed prior to the first dose of study drug. If the Investigator deems that it is necessary, consultation with a TB expert could be considered.

**Note: Rifampicin or Rifapentine is Not Allowed for TB prophylaxis**

In Period 2, when study drug has been unblinded, rifampicin or rifapentine are allowed for TB prophylaxis for subjects not receiving upadacitinib.

Subjects with a prior history of latent TB that have documented completion of a full course of anti-TB therapy within 1 year prior to first study drug administration will be allowed to enter the study provided nothing has changed in the subject's medical history to warrant repeat treatment.

Obtain a CXR annually for subjects with newly identified TB risk factors as determined by the TB risk assessment form ([Appendix I](#)), or for subjects living in areas endemic for TB or for subjects with newly positive PPD or QuantiFERON-TB Gold test.

For subjects with seroconversion on an annual TB test, if a CXR cannot be done due to state of emergency or pandemic situation like COVID-19, the Investigator should contact

the AbbVie TA MD to determine if the subject may continue on study drug. CXR should be performed as soon as restrictions allow at the study site or local hospital/facility.

Subjects with a documented completion of a full course of anti-TB therapy greater than 1 year prior to first study drug administration may be allowed to enter the study only after consultation with the AbbVie Therapeutic Area Medical Director.

Newly initiated prophylactic treatment should be captured in the eCRF and in the source documents. Prior therapy should be captured in the eCRF.

During the study, subjects with new evidence of latent TB should initiate prophylactic treatment immediately per local guidelines. Study drug(s) should **not** be withheld and Isoniazid and/or rifampin/rifapentine should be initiated and 2 to 4 weeks later (per local guidelines), subject should be re-evaluated (unscheduled visit) for signs and symptoms of isoniazid toxicity.

In Period 2, when study drug has been unblinded, rifampicin or rifapentine are allowed for TB prophylaxis for subjects not receiving upadacitinib.

If the subject is experiencing signs or symptoms suspicious for TB or something has changed in the subject's medical history to warrant a repeat test before the next scheduled annual TB re-test, the case (including the TB test results) must be discussed with the AbbVie Therapeutic Area Medical Director.

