11. Systemic use of known strong cytochrome P450 3A (CYP3A) inhibitors or strong CYP3A inducers from Screening through the end of the study (refer to [Table 1](#) for examples of commonly used strong CYP3A inhibitors and inducers).
12. Receipt of any live vaccine within 4 weeks prior to the first dose of study drug, or expected need of live vaccination during study participation including at least 4 weeks after the last dose of study drug.
13. History of any malignancy except for successfully treated NMSC or localized carcinoma in situ of the cervix.
14. History of clinically significant (per Investigator's judgment) drug or alcohol abuse within the last 6 months.
15. History of gastrointestinal perforation (other than appendicitis or penetrating injury), diverticulitis, or significantly increased risk for GI perforation per investigator judgment.
16. Conditions that could interfere with drug absorption including but not limited to short bowel syndrome.
17. Subject has been a previous recipient of an organ transplant.
18. History of clinically significant medical conditions or any other reason that in the opinion of the Investigator would interfere with the subject's participation in this study or would make the subject an unsuitable candidate to receive study drug.
19. Active infection(s) requiring treatment with parenteral anti-infectives within 30 days, or oral anti-infectives within 14 days prior the first dose of study drug.
20. History of an allergic reaction or significant sensitivity to constituents of the study drug(s) (and their excipients) and/or other products in the same class.
21. Laboratory values meeting the following criteria within the Screening period prior to the first dose of study drug:
  - Serum aspartate transaminase (AST)  $> 2 \times$  ULN
  - Serum alanine transaminase (ALT)  $> 2 \times$  ULN

- Estimated glomerular filtration rate (GFR) by simplified 4-variable Modification of Diet in Renal Disease (MDRD) formula  $< 40 \text{ mL/min/1.73 m}^2$
  - Total white blood cell count (WBC)  $< 2,500/\mu\text{L}$
  - Absolute neutrophil count (ANC)  $< 1,500/\mu\text{L}$
  - Platelet count  $< 100,000/\mu\text{L}$
  - Absolute lymphocyte count  $< 800/\mu\text{L}$
  - Hemoglobin  $< 10 \text{ g/dL}$
22. History of any of the following cardiovascular conditions:
- Moderate to severe congestive heart failure (New York Heart Association class III or IV),

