### **Rationale for Exclusion Criteria**

- |               |  |
|---------------|--|
| 1 – 2         | To select the appropriate subject population   |
| 7 – 8         | Upadacitinib is teratogenic in both rats and rabbits. The effect of upadacitinib on human pregnancy and reproduction is unknown. |
| 3 – 6, 9 – 24 | To ensure safety of the subjects throughout the study  |

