### **Traditional Chinese Medicine**

Traditional oral Chinese medicine cannot be initiated or changed during the study as these may interfere with upadacitinib metabolism and exposure and may impact efficacy and safety of upadacitinib treatment.

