### **Strong CYP3A Inhibitors or Inducers**

Systemic use of known strong CYP3A inhibitors or strong CYP3A inducers is excluded from the Screening Visit through the end of the study (i.e., Periods 1 and 2). The most common strong CYP3A inhibitors and inducers are listed in Table 1.

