**Table 1. Examples of Commonly Used Strong CYP3A Inhibitors and Inducers**

Strong CYP3A Inhibitors	Strong CYP3A Inducers
Boceprevir Cobicistat Clarithromycin Conivaptan Grapefruit (fruit or juice) Indinavir Itraconazole Ketoconazole Lopinavir/Ritonavir Mibefradil Nefazodone Nelfinavir Posaconazole Ritonavir Saquinavir Telaprevir Telithromycin Troleandomycin Voriconazole	Avasimibe Carbamazepine Phenytoin Rifampin Rifapentine St. John's Wort

In Period 2, when study drug has been unblinded, systemic use of known strong CYP3A inhibitors or strong CYP3A inducers is permitted for subjects not receiving upadacitinib.

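### The on-study latent-TB instruction offers rifampin/rifapentine with study drug continued and sets no limit, contrary to the protocol's own bar on these drugs

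*Protocol*

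**What the plan says.** The instruction is in Protocol Section 5.3.1.1, under TB Prophylaxis. It covers subjects in whom latent TB is newly found during the study. Prophylaxis is to start at once under local guidelines, and study drug should not be "withheld and Isoniazid and/or rifampin/rifapentine should be initiated and 2 to 4 weeks later" the subject is seen again to look for isoniazid toxicity.

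The same drugs are dealt with in five other places in the protocol:

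- The Note in the same part of Section 5.3.1.1: "Rifampicin or Rifapentine is Not Allowed for TB prophylaxis".
- The exception in Section 5.3.1.1, given once under the Note and again directly after the disputed sentence: in Period 2, once study drug is unblinded, "rifampicin or rifapentine are allowed for TB prophylaxis for subjects not receiving upadacitinib".
- Section 5.2.2, exclusion criterion 11: "Systemic use of known strong cytochrome P450 3A (CYP3A) inhibitors or strong CYP3A inducers from Screening through the end of the study".
- Section 5.2.3.2: "Systemic use of known strong CYP3A inhibitors or strong CYP3A inducers is excluded from the Screening Visit through the end of the study", stated there to cover both periods.
- Table 1, whose list of strong inducers includes "Avasimibe Carbamazepine Phenytoin Rifampin Rifapentine". The text below the table gives the same exception for unblinded Period 2.

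**The concern.** The disputed sentence tells sites how to treat a subject and is not background text. It says which drugs to start, says to start them immediately, and says to keep study drug going. Taken alone, it lets a site give a rifamycin to a subject who is taking upadacitinib, which the rest of the protocol forbids. Because the choice follows local guidelines, a site whose guidelines favour a rifamycin is pointed to the barred drug. Section 5.4.1 also makes non-compliance with TB prophylaxis a reason to stop study drug, so sites have cause to act quickly.

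What is at stake is subject safety. The rationale given for a group of exclusion criteria that includes criterion 11 is "To ensure safety of the subjects throughout the study".

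**Working it through.** The plan states no figure on this point. The check sets the sentence against the bar in each situation that the study can produce.

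1. **Blinded treatment, any arm (Period 1, or Period 2 before unblinding).** The sentence offers a rifamycin. The Note and Section 5.2.3.2 forbid it for everyone, because the exception requires unblinding. Conflict.
2. **Unblinded Period 2, subject on upadacitinib.** The sentence offers a rifamycin. The Note, Section 5.2.3.2 and Table 1 forbid it, because the exception requires that the subject is not on upadacitinib. Conflict.
3. **Unblinded Period 2, subject not on upadacitinib.** The sentence offers a rifamycin and the exception allows it. No conflict.

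The sentence therefore agrees with the rest of the protocol in one situation of three. Reading the Note as applying to Screening only does not remove the conflict. The exception beneath it speaks of Period 2, so the Note reaches beyond Screening, and Section 5.2.3.2 bars strong inducers in both periods in any case.

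**How much of this is still ahead.** Situation 1 is historical as far as Period 1 goes: Section 5.5.5.2 says that all subjects had reached the end of Period 1 as of September 2018. New latent TB would mostly be found at scheduled re-tests of subjects who had tested negative. Appendices D and F place these at Week 48, Week 96 and every 48 weeks through Week 240, which gives Weeks 48, 96, 144, 192 and 240, or 5 tests. The synopsis is dated 03 December 2020.

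- Latest reading of September 2018: 30 September 2018 to 03 December 2020 is 795 days, and 795 / 7 = 113.6 weeks.
- A continuing subject was then at Week 48 + 113.6 = 161.6 or later. If the Week 48 visit fell 7 days early, within its window, this becomes Week 160.6.
- Only Weeks 192 and 240 lie beyond that point, so at most 2 of the 5 scheduled tests remained. Delayed or unscheduled tests would add to this.

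This counts tests, not subjects. The documents give neither a conversion rate nor the number of subjects still on upadacitinib and test-negative, so the number affected cannot be worked out.

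**The case against.** The strongest reply is that the protocol, read as a whole, gives one rule. The Note is general, the exception stands in the very next paragraph, and a permission for those off upadacitinib would be pointless if everyone already had it. The words and/or allow isoniazid alone, and the only toxicity named for follow-up is that of isoniazid. Section 5.2.3 sends questions on concomitant therapy to the sponsor's medical director. Section 5.4.1 requires study drug to stop if a prohibited medicine has been introduced and the medical director judges that continuing would endanger the subject. Appendix F has concomitant therapy reviewed at each Period 2 visit.

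Most of this stands, and it is why the correction is minor. It does not remove the conflict. The following paragraph grants a permission without saying that it limits the sentence before it, and the safeguards work only if a site sees a question to ask or after the drug has been started.

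A reader might infer more than the documents support:

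- *That the protocol requires a rifamycin alongside upadacitinib.* It offers one, and isoniazid alone complies.
- *That planned arm sizes measure how many subjects are exposed to the error.* They do not count subjects who are still on drug, test-negative and newly converting. The exception also covers anyone who has stopped upadacitinib, so it is not confined to the methotrexate arm.
- *That a site following the sentence would have to record a deviation.* SAP Section 6.4 lists categories for summary tables and does not say what a site records.
- *That open-label supply tells every site who is on upadacitinib.* The Amendment 6 statement in Section 5.5.3 covers the 15 mg, 30 mg and methotrexate groups and does not name the 7.5 mg group in Japan.
- *That the protocol describes the harm.* It gives no size for this interaction. Its remark on altered upadacitinib exposure in Section 5.2.3.1 concerns traditional Chinese medicine.
- *That Appendix F footnote d is a second error.* It names no drug and refers back to Section 5.3.1.1.

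**Conclusion.** The sentence is wrong as written. It offers two drugs that the protocol prohibits, and it leaves out the limit that every other provision carries. This is a minor correction to safety text, because the intended rule can be recovered from the adjoining paragraph and a compliant option stands in the same sentence.

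The number affected is unknown and probably small. That judgement rests on the few scheduled re-tests left after the synopsis date and on the assumption that many sites would choose isoniazid or notice the Note; the documents do not test that assumption. Nothing changes in the analysis. Concomitant medications are already tabulated (SAP Section 6.3), and SAP Section 11.1 states that the primary efficacy analysis and Period 1 reporting were complete.

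**What to change.** Keep the direction not to withhold study drug, and replace the drug clause in Section 5.3.1.1 with: *isoniazid (or another non-rifamycin regimen per local guidelines) should be initiated; rifampin/rifapentine may be used only in unblinded Period 2 for subjects not receiving upadacitinib.* Send sites a short notice of the change. The existing medical-director contact can handle a case where local guidelines favour a rifamycin.

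Appendix F footnote d needs no separate change. The cost is one sentence and one site letter, with no new data.
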